#### **5.3.2. Obinutuzumab**

Refer to the obinutuzumab Investigator's Brochure for additional information.

##### **5.3.2.1. Formulation/Packaging/Storage**

Obinutuzumab is manufactured by Roche/Genentech, a member of the Roche Group, and is supplied as 1000 mg/40 mL (25 mg/mL) single-use vials containing preservative-free solution (NDC 50242-070-01) are stable at 2°C to 8°C (36°F to 46°F). Do not use beyond expiration date stamped on carton. Obinutuzumab vials should be protected from light. DO NOT FREEZE. DO NOT SHAKE.

For the diluted product, chemical and physical stability have been demonstrated in 0.9% NaCl at concentrations of 0.4 mg/mL to 20 mg/mL for 24 hours at 2°C to 8°C (36°F to 46°F) followed by 48 hours (including infusion time) at room temperature ( $\leq 30^{\circ}\text{C}/86^{\circ}\text{F}$ ). Obinutuzumab does not contain antimicrobial preservatives. Therefore care must be taken to ensure that the solution for infusion is not microbiologically compromised during preparation. The solution for infusion should be used immediately. If not used immediately, the prepared solution may be stored up to 24 hours at 2–8°C. No incompatibilities between obinutuzumab and polyvinyl chloride or polyolefin infusion materials have been observed in concentration ranges from 0.4 mg/mL to 20.0 mg/mL after dilution of Obinutuzumab with 0.9% sodium chloride.

##### **5.3.2.2. Premedication**

All subjects should be premedicated with acetaminophen/paracetamol to reduce the risk of obinutuzumab related infusion reactions, as detailed in Table 2 below.

Subjects with a history of cardiac disease should be monitored closely. In addition these subjects should be hydrated with caution in order to prevent a potential fluid overload. Hypotension may occur during obinutuzumab administration. Consider withholding antihypertensive treatments for

12 hours prior to and throughout each obinutuzumab infusion and for the first hour after administration.

**Table 2: Premedication to be Administered Before Obinutuzumab Infusion to Reduce the Risk of Infusion Related Reactions (Mandatory for CLL Subjects Receiving the First Dose)**

Day of Treatment Cycle	Subjects requiring premedication	Premedication	Administration
Cycle 1: Day 1	All subjects	Intravenous corticosteroid 	Completed at least 1 hour prior to obinutuzumab infusion.
		Oral analgesic/anti-pyretic 	At least 30 minutes before obinutuzumab infusion.
		Anti-histaminic drug 	
Cycle 1: Day 2	All subjects	Intravenous corticosteroid 	Completed at least 1 hour prior to obinutuzumab infusion.
		Oral analgesic/anti-pyretic 	At least 30 minutes before obinutuzumab infusion.
		Anti-histaminic drug 	
Cycle 1: Day 8, Day 15	Subjects with a Grade 3 IRR with the previous infusion OR subjects with lymphocyte counts $>25 \times 10^9/L$ prior to next treatment	Intravenous corticosteroid 	Completed at least 1 hour prior to obinutuzumab infusion.
Cycles 2-6: Day 1	All subjects	Oral analgesic/anti-pyretic 	At least 30 minutes before obinutuzumab infusion.
	Subjects with an IRR (Grade 1 or more) with the previous infusion	Anti-histaminic drug 	

1. 20 mg dexamethasone or 80 mg methylprednisolone or equivalent given intravenously. Hydrocortisone should not be used as it has not been effective in reducing rates of IRR.

2. eg, 1000 mg acetaminophen/paracetamol

3. eg, 50 mg diphenhydramine

### **Tumor Lysis Syndrome (TLS)**

Subjects with a high tumor burden (white blood cell count  $\geq 25 \times 10^9/L$  or bulky lymphadenopathy) must receive prophylaxis for TLS prior to the initiation of treatment (McBride and Westervelt 2012). This includes appropriate hydration, consisting of a fluid intake of approximately 3 liters per day, starting 1–2 days before the first dose of obinutuzumab. All such subjects with high tumor burden must be treated with allopurinol or a suitable alternative treatment (ie, rasburicase) starting at least 72 hours prior to the first infusion of obinutuzumab (Cycle 1, Day 1). These measures may also be extended to other subjects considered at risk of TLS in the judgment of the investigator.

Subjects still considered at risk for TLS because of persistently high tumor burden (ie, peripheral blood lymphocyte counts  $\geq 25 \times 10^9/L$ ) before the second and subsequent infusions of obinutuzumab should receive continuous TLS prophylaxis with allopurinol or a suitable alternative (ie, rasburicase) and adequate hydration until the risk is abated, as determined by the investigator.

All subjects considered at risk by the investigator should be carefully monitored during the initial days of study treatment with a special focus on renal function, potassium, and uric acid values.

Any additional guidelines should be followed according to institutional practice (McBride and Westervelt 2012).

### **Neutropenia**

Subjects with neutropenia are strongly recommended to receive antimicrobial prophylaxis throughout the treatment period. Antiviral and antifungal prophylaxis should be considered.

#### **5.3.2.3. Dosage Regimen and Administration**

Obinutuzumab should be diluted in 0.9% Sodium Chloride Injection, USP or local equivalent. Do not use other diluents, such as 5% Dextrose in Water. Do not co-administer or mix obinutuzumab with any other intravenous drug.

Each dose of obinutuzumab is 1000 mg, with the exception of the first infusions in Cycle 1, which are administered on Day 1 (100 mg) and Day 2 (900 mg) (Gazyva USPI 2013). Obinutuzumab should be administered as an IV infusion, according to the following schedule:

**Table 3: Obinutuzumab Dosing Schedule**

Day of Treatment Cycle		Dose of Obinutuzumab	Rate of infusion (in the absence of infusion reactions/hypersensitivity during previous infusions)
Cycle 1	Day 1	100 mg	Administer at 25 mg/hr over 4 hours. Do not increase the infusion rate
	Day 2	900 mg	Administer at 50 mg/hr. The rate of the infusion can be escalated in increments of 50 mg/hr every 30 minutes to a maximum rate of 400 mg/hr
	Day 8	1000 mg	Infusions can be started at a rate of 100 mg/hr and increased by 100 mg/hr increments every 30 minutes to a maximum of 400 mg/hr.
	Day 15	1000 mg	
Cycle 2-6	Day 1	1000 mg	

If a subject experiences an infusion reaction of any grade during infusion, adjust the infusion as follows:

- Grade 4 (life threatening): Stop infusion immediately and permanently discontinue obinutuzumab therapy.
- Grade 3 (severe): Interrupt infusion and manage symptoms. Upon resolution of symptoms, consider restarting obinutuzumab infusion at no more than half the previous rate (the rate being used at the time that the infusion reaction occurred) and, if subject does not experience any further infusion reaction symptoms, infusion rate escalation may resume at the increments and intervals as appropriate for the treatment cycle dose. Permanently discontinue treatment if subject experience a Grade 3 infusion related symptom at re-challenge.
- Grade 1–2 (mild to moderate): Reduce infusion rate or interrupt infusion and treat symptoms. Upon resolution of symptoms, continue or resume infusion and, if subject does not experience any further infusion reaction symptoms, infusion rate escalation may resume at the increments and intervals as appropriate for the treatment cycle dose.

#### **5.3.2.4. Dose Delay**

Treatment with obinutuzumab should be held for any unmanageable, potentially obinutuzumab-related toxicity which merits a dose delay, in the opinion of the investigator. In particular, this includes subjects experiencing an infection, Grade 3 or 4 cytopenia (according to Grading Scale for hematologic toxicities in CLL studies, Appendix D), or a Grade  $\geq 2$  non-hematologic toxicity. In principle, obinutuzumab therapy should be withheld until toxicity has resolved to at least Grade 1. In certain circumstances, therapy with obinutuzumab may be re-initiated despite an ongoing toxicity which has not resolved to Grade  $\leq 1$ , providing it is clinically appropriate to do so, in the opinion of the investigator and that this has been discussed first with the Medical Monitor.

Obinutuzumab should be discontinued if progressive multifocal leukoencephalopathy (PML) is suspected.

Any other clinically important events where dose delays may be considered appropriate by the investigator should be discussed with the Medical Monitor.

Obinutuzumab may be held for a maximum of 28 days from expected dose due to toxicity. Study treatment should be discontinued in the event of a toxicity lasting  $>28$  days, unless reviewed and approved by the Medical Monitor.

#### **5.3.2.5. Obinutuzumab Dose Modifications**

##### **Thrombocytopenia**

Severe and life-threatening thrombocytopenia has been observed during treatment with obinutuzumab. In CLL patients exposed to chlorambucil and obinutuzumab, fatal hemorrhagic

events have been reported in Cycle 1. A clear relationship between thrombocytopenia and hemorrhagic events has not been established.

Subjects should be closely monitored for thrombocytopenia, especially during the first cycle; regular laboratory tests should be performed until the event resolves, and dose delays should be considered in case of severe or life-threatening thrombocytopenia. Transfusion of blood products (ie, platelet transfusion) according to institutional practice is at the discretion of the treating physician. Use of all concomitant therapies, which could possibly worsen thrombocytopenia-related events such as platelet inhibitors and anticoagulants, should also be taken into consideration, especially during the first cycle.

Toxicity	Obinutuzumab
Severe thrombocytopenia (platelets <10,000/<math>\mu</math>L) and/or symptomatic bleeding in patients who are not receiving concomitant anticoagulants or platelet inhibitors	
 
• Hold obinutuzumab in case of severe thrombocytopenia (platelets <10,000/<math>\mu</math>L) or symptomatic bleeding (irrespective of platelet count) until it resolves. If Cycle 1 Day 8 is delayed then skip Day 8 and administer Day 15 as previously scheduled (if symptomatic bleeding has resolved).
 
• If Cycle 1 Day 15 is delayed then skip Day 15 dosing and administer Cycle 2 Day 1 of obinutuzumab as scheduled (if symptomatic bleeding has resolved).
 

Thrombocytopenia with platelets <20,000/<math>\mu</math>L and/or symptomatic bleeding in patients who are receiving concomitant anticoagulants or platelet inhibitors	
 
• Hold obinutuzumab in case of platelets <20,000/<math>\mu</math>L or symptomatic bleeding (irrespective of platelet count) until it resolves. If Cycle 1 Day 8 is delayed then skip Day 8 and administer Day 15 as previously scheduled (if symptomatic bleeding has resolved). If Cycle 1 Day 15 is delayed then skip Day 15 dosing and administer Cycle 2 Day 1 of obinutuzumab as scheduled (if symptomatic bleeding has resolved).
 
• At the discretion of the study investigator, for patients who are on LMWH, when thrombocytopenia with platelets <20,000/<math>\mu</math>L develops, reduce the dose of LMWH used.
 
• At the discretion of the study investigator, for patients who are on platelet inhibitors, when thrombocytopenia with platelets <20,000/<math>\mu</math>L develops, consideration should be given to temporarily pause their use
 

If the clinical condition of subject requires the use of concomitant anticoagulants, the subjects are at increased risk of bleeding when thrombocytopenia with platelets <20,000/ $\mu$ L develops.

While subjects are on both ibrutinib and obinutuzumab, dose modification / hold for each individual study drug should follow criteria set forth under that drug.

While subjects are on both chlorambucil and obinutuzumab, dose modification / hold for each individual study drug should follow criteria set forth under that drug.

### **5.3.2.6. Continuation of Obinutuzumab in the Event of Discontinuation of Concomitant Ibrutinib/Chlorambucil**

In the event of permanent discontinuation of concomitant ibrutinib (Arm A) or chlorambucil (Arm B) for any reason, treatment with obinutuzumab will be continued to complete a total of 6 cycles of therapy with obinutuzumab.

### **5.3.3. Chlorambucil**

#### **5.3.3.1. Formulation/Packaging/Storage**

Chlorambucil (LEUKERAN®) is manufactured by Aspen and is supplied as brown, biconvex tablets containing 2 mg chlorambucil in amber glass bottles with child-resistant closures. The recommended storage condition for chlorambucil tablets is in a refrigerator, 2° to 8°C (36° to 46°F).

#### **5.3.3.2. Dosage and Administration**

Chlorambucil will be administered orally at a dose of 0.5 mg/kg body weight, on Days 1 and 15 of each cycle. On Day 1, chlorambucil will be given as soon as the subject comes into clinic. Pre-medications and obinutuzumab will then be given as outlined in Table 2.

Chlorambucil will be administered in the clinic on days which coincide with concomitant obinutuzumab (Days 1 + 15 of Cycle 1 and Day1 of Cycles 2-6) and will be issued to the subject for home administration on other occasions (Day 15 of Cycles 2-6).

For subjects who have difficulty taking the entire dose of chlorambucil at a single time, the pills may be split up into 2 to 3 batches to be taken over 8 hours on the same day. The dose should not be taken over more than one day.

Unused chlorambucil dispensed during the previous visit must be returned to the site and drug accountability records (Section 12.8) updated at each visit. Returned tablets must not be re-dispensed to anyone.

#### **5.3.3.3. Dose Delay and Modifications**

Treatment with chlorambucil should be held for any unmanageable, potentially study drug-related toxicity that is Grade 3 or higher in severity. Chlorambucil may be held for toxicity up to a maximum of 28 consecutive days, after which it should be discontinued, unless reviewed and approved by the Medical Monitor. Guidelines for dose modifications are outlined in Table 4 due to AE irrespective of causality. At the investigator's discretion, a subject's dose may be re-escalated after 2 cycles of a dose reduction in the absence of a recurrence of the toxicity that led to the reduction.

If institutional guidelines for chlorambucil dose modifications are different from these guidelines, variances will be permitted after discussion with the Medical Monitor.

**Table 4: Dose Modifications for Chlorambucil Due to Toxicity**

Toxicity	Chlorambucil Dose Action
ANC <500/ $\mu$ L for >7 days	Hold until recovery to >1,000/ $\mu$ L; restart at a 25% decrement of the original dose and at each occurrence
Platelets <50,000/ $\mu$ L with bleeding	Hold until recovery to >50,000/ $\mu$ L and resolution of bleeding; restart at full dose
Platelets <25,000/ $\mu$ L with or without bleeding (ongoing or at any time during previous cycle)	Hold until recovery to >50,000/ $\mu$ L and resolution of bleeding; restart at a 25% decrement of the original dose and at each occurrence
Unmanageable Grade 3 nonhematologic toxicity	Hold until recovery to Grade $\leq$ 1 or baseline; restart at original dose
Grade 4 nonhematologic toxicity (ongoing or at any time during previous cycle)	Hold until recovery to Grade $\leq$ 1 or baseline; restart at a 25% decrement of the original dose and at each occurrence
Repetitive or intractable Grade 3/4 nonhematologic toxicity or any Grade 4 toxicity deemed related to study drug	Discontinue study drug

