**Table 1: Ibrutinib Dose Modifications**

Occurrence	Action to be Taken
First	Withhold study drug until recovery to Grade $\leq$ 1 or baseline; may restart at original dose level
Second	Withhold study drug until recovery to Grade $\leq$ 1 or baseline; may restart at 1 dose level lower (ie, 280 mg/day for 420 mg/day dose)
Third	Withhold study drug until recovery to Grade $\leq$ 1 or baseline; may restart at 1 dose level lower (ie, 140 mg/day for 420 mg/day dose)
Fourth	Discontinue study drug

Study treatment interruptions, dose reductions or modifications, or any other changes in study drug administration should be recorded in the clinical database. Study treatment should be discontinued in the event of an ibrutinib toxicity lasting more than 28 days, unless reviewed and approved by the Medical Monitor. Note: Temporary withholding of study drug for as little as 7 days can cause a transient worsening of disease and/or of constitutional symptoms. Study drug should be re-started as soon as clinically appropriate.

After a dose reduction, dose escalations of ibrutinib to the previous higher dose may be considered after consultation with the Medical Monitor if the event does not recur after at least one cycle of the lower dose.

For required dose modification for hepatic impairment refer to Section 5.3.1.6 and for concomitant treatment with CYP3A inhibitors refer to Section 6.2.1.

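### Chlorambucil Table 4 gives two incompatible actions, restart at a reduced dose or stop, for a Grade 4 nonhematologic toxicity deemed related to the drug

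*Protocol*

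**What the plan says.** Table 4 of the protocol (Section 5.3.3.3) has six rows. Counting from the top, rows 1 to 3 deal with neutrophil and platelet counts, row 4 with unmanageable Grade 3 nonhematologic toxicity, and rows 5 and 6 are at issue here.

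- Row 5 is triggered by "Grade 4 nonhematologic toxicity (ongoing or at any time during previous cycle"). Its action is to hold until recovery and then "restart at a 25% decrement of the original dose and at each occurrence".
- Row 6 is triggered by "Repetitive or intractable Grade 3/4 nonhematologic toxicity or any Grade 4 toxicity deemed related to study drug". Its action is to stop the drug for good.

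The paragraph before the table says: "Guidelines for dose modifications are outlined in Table 4 due to AE irrespective of causality". It also limits interruptions: "Chlorambucil may be held for toxicity up to a maximum of 28 consecutive days", unless the Medical Monitor approves longer. Where an institution's own chlorambucil guidelines differ, "variances will be permitted after discussion with the Medical Monitor".

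Section 5.3.2.5 adds, for subjects on both drugs, that "dose modification / hold for each individual study drug should follow criteria set forth under that drug", which brings the reader back to Table 4. Section 5.3.2.6 keeps obinutuzumab going to six cycles if chlorambucil is stopped.

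**The concern.** Row 5 is limited neither by causality nor to a first event. Row 6 covers every Grade 4 toxicity attributed to the drug. A related Grade 4 nonhematologic event therefore falls in both rows, one leading to re-treatment and the other to permanent discontinuation.

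This is a safety instruction for a cytotoxic drug. A site that restarts may re-expose a subject to a drug that row 6 says to stop. A site that stops may end control treatment that row 5 says to resume. Each can point to protocol text, so neither action would clearly be a deviation, and Arm B chlorambucil exposure could differ between sites for the same event.

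The same protocol shows that a clear rule was possible. Ibrutinib Table 1 gives one action per occurrence: after the first, the drug "may restart at original dose level"; the second and third lead to lower doses and the fourth to discontinuation.

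**Working it through.** The plan states no figure to reproduce. The main check sets cases against the row triggers.

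| Case (Grade 4, nonhematologic) | Row 5 | Row 6 | Result |
|---|---|---|---|
| First event, related | Met: restart lower | Met: stop | Conflict |
| First event, unrelated, not intractable | Met: restart lower | Not met | Clear |
| Second event, unrelated, same toxicity | Met: restart lower again | Met if one recurrence counts as repetitive | Ambiguous |
| Second event, unrelated, different toxicity | Met: restart lower again | Met only if repetitive counts any Grade 4 event | Ambiguous |

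**Does other text settle the first case?** The sentence introducing Table 4 sets causality aside for the table as a whole, so it gives no support for confining row 5 to unrelated events. The Medical Monitor clause concerns institutional guidelines that differ from the protocol, not two protocol rows that differ from each other. Section 5.3.2.5 returns the reader to the same table. Nothing states an order of precedence.

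**What the choice means for one subject (illustration only).** Inputs: 0.5 mg/kg on Days 1 and 15 for six cycles (Section 5.3.3.2), so 2 × 6 = 12 planned doses. A 25% cut gives 0.5 × 0.75 = 0.375 mg/kg. Event timing is assumed. The calculation also assumes no recurrence and no re-escalation. In the last column one 28-day hold costs two doses that are not made up.

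| Event after | Row 6: stop | Row 5: no dose missed | Row 5: 28-day hold |
|---|---|---|---|
| Cycle 1 | 2/12 = 16.7% | (2 + 0.75×10)/12 = 79.2% | (2 + 0.75×8)/12 = 66.7% |
| Cycle 3 | 6/12 = 50.0% | (6 + 0.75×6)/12 = 87.5% | (6 + 0.75×4)/12 = 75.0% |
| Cycle 5 | 10/12 = 83.3% | (10 + 0.75×2)/12 = 95.8% | 10/12 = 83.3% |

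The gap is large for an early event and falls to zero for a late event with a full hold. The 28-day column is not a lower bound, because longer holds can be approved.

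**The case against.** The best defence is that row 6 is the specific stop rule and overrides row 5. Row 6 is the only row that ends treatment, and it carries its own causality condition. If row 5 prevailed, the related-toxicity clause of row 6 would do nothing for nonhematologic events. If row 6 prevails, row 5 still governs unrelated events. That reading is natural and also the safer one. It stands as the likely intent, but the protocol does not state it and the introductory sentence points the other way, so a site is left to infer a safety rule.

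There are safeguards. Both rows interrupt dosing at once, row 5 permits restart only after recovery, and Section 9.2 lets the investigator stop treatment in the subject's interest. These reduce the risk. They do not say which row applies.

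A reader might infer that a repeat Grade 4 event is an equally plain contradiction. The documents do not support that. The recurrence wording in row 5 also appears in rows 1 and 3 and can refer to separate, different events, while repetitive in row 6 can mean the same toxicity returning. The term is undefined, so this is an ambiguity.

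Materiality is limited. No Grade 4 rate is given, and Section 5.3.3.4 describes the common chlorambucil toxicities as hematologic. The edit may also come too late: Section 10.7.2.3 uses 229 randomized subjects against about 212 planned in Section 10.3, and chlorambucil runs for at most six 28-day cycles. That suggests, but does not prove, that Arm B dosing is over.

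**Conclusion.** The point holds for a Grade 4 nonhematologic toxicity deemed related to chlorambucil: Table 4 prescribes both a reduced-dose restart and permanent discontinuation, and no text ranks them. For repeat events there is a lesser ambiguity that rests on an undefined word.

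The number of subjects affected is unknown and probably small. The dose percentages depend on assumed timings and describe a single affected subject. A reader might take them as evidence of weakened control treatment or a biased PFS comparison. The documents give no event rate from which to argue that, and no effect on PFS, power or alpha is claimed. The case for acting is that a safety rule should give one instruction, and that correcting this one is cheap if dosing is still under way.

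**What to change.** If Arm B dosing is ongoing, and subject to clinical confirmation:

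1. Limit row 5 to Grade 4 nonhematologic toxicity not deemed related to the drug. Keep its recurrence wording, for separate, different events.
2. Add a note to Table 4 that row 6 overrides rows 4 and 5; that repetitive means recurrence of the same toxicity after restart; and that a cytopenia meeting a trigger in rows 1 to 3 follows that row.
3. Amend Section 5.3.3.3 so that the table applies whatever the cause except where a row says otherwise.

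The note should not exempt neutropenia and thrombocytopenia from row 6 altogether. Rows 1 to 3 do not cover every Grade 4 count in Appendix D. A neutrophil count below 500/µL lasting 7 days or less misses row 1. A platelet fall from 200,000 to 45,000/µL without bleeding is a 155,000/200,000 = 77.5% drop, hence Grade 4, yet misses rows 2 and 3. If related, such events now fall literally under row 6, and a full exemption would leave them in no row. Keeping them there does mean that a short related neutropenia is treated more severely than one lasting over 7 days, so the clinical team should confirm that this is intended.

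The cost is a short amendment and a site memo.

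If Arm B dosing is complete, no edit is needed. SAP Section 3.4 already summarizes chlorambucil exposure, relative dose intensity and reductions due to adverse events, and SAP Section 5, Table 2, covers related events and those leading to discontinuation or dose reduction. These largely meet the reporting need.
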